**Exclusion Criteria:**

- Inability to comprehend written and/or spoken English
- Inability to provide informed consent
- Medical illness precluding laparoscopy
- Need for concomitant surgeries not related to pelvic organ prolapse or incontinence
- Sacrocolpopexy
- Patients desiring uterine preservation (hysteropexy)

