**Background and Significance:**

For young women who are sexually active with symptomatic pelvic organ prolapse, reconstruction with a sacrocolpopexy procedure is beneficial because the success rates are high as the procedure adequately restores support of the vaginal apex and maintains vaginal length (Walters). Minimally invasive abdominal sacrocolpopexy has become an alternative to open abdominal sacrocolpopexy as this mode of surgery bridges the gap between the advantages of vaginal surgery, namely decreased morbidity and faster patient recovery, with the surgical success rates of abdominal sacrocolpopexy (Ganatra).

Sacrocolpopexy involves suspension of the vagina to the anterior longitudinal ligament of the sacrum at the level of S1 using a bridging graft which can be made of biologic or synthetic materials. The graft is sutured to the anterior as well as the posterior vagina and then attached to the anterior longitudinal ligament of the sacrum. The surgery can be performed for uterovaginal prolapse or post-hysterectomy vaginal vault prolapse. In cases of uterovaginal prolapse, hysterectomy is often performed unless uterine preserving surgery is desired and a hysteropexy is performed. When concurrent hysterectomy is done, a supracervical or total approach may be taken.

In 2014, there was a de facto change in practice patterns after the Food and Drug Administration advised against power morcellation for extraction of the uterine specimen after minimally invasive supracervical hysterectomy. At that time, surgeons performing prolapse surgery had to choose to continue performing concurrent supracervical hysterectomy at the time of sacrocolpopexy using an extended abdominal incision to remove the uterus. An alternative solution became to perform total vaginal hysterectomy followed by a combination of mesh attachment vaginally (to the vagina) and laparoscopically (to the sacrum) versus mesh attachment performed laparoscopically only

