(to the vagina and sacrum). Very few studies have looked at the outcomes of these two ways to perform minimally invasive sacrocolpopexy with concurrent hysterectomy. One study published by Nosti et al. did compare the two groups retrospectively and found that there was no difference in mesh-related complications between the groups and that vaginal mesh attachment following vaginal hysterectomy decreased operative time significantly with no differences in intraoperative complications, reoperation for recurrent prolapse, and subjective or objective outcomes compared to concurrent supracervical hysterectomy (Nosti). In our practice, both techniques are currently used, and while we also believe there are no differences in complications and outcomes between the two modes of surgery, anecdotally our group feels that surgical time may be the same between the two types of prolapse repairs.

Cost of health care has become a hot topic in the medical community. One of the focuses of cost containment in medicine has centered around operating room efficiency. Several studies have looked at OR time nonutilization (Weinbaum) in order to determine the economic value of saving OR time. Surgeons can make significant contributions to these types of savings by reducing equipment needs, facilitating case set-up times, and focusing on intraoperative efficiency. This includes choosing a mode of hysterectomy and technique for mesh attachment at the time of sacrocolpopexy that may make the entire procedure faster and more efficient.

Given the sparse data that exist, it remains unclear if one type of concurrent hysterectomy and subsequent mesh attachment at the time of sacrocolpopexy is more efficient. Furthermore, because no prospective studies exist, we also do not know with any degree of certainty if one approach reduces the risk of intraoperative and postoperative mesh-related complications as well as the risk of prolapse recurrence. Therefore, the primary objective of the proposed study is to determine the difference in surgical time between minimally invasive (laparoscopic) sacrocolpopexy performed with concurrent vaginal hysterectomy versus laparoscopic supracervical hysterectomy. The secondary objectives are to determine if there are differences in intraoperative adverse events and postoperative mesh-related complications and prolapse recurrence between the groups.

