**Inclusion Criteria:**

- Age  $\geq$  18, who are to undergo laparoscopic sacrocolpopexy for uterovaginal prolapse and desire concurrent hysterectomy at the time of surgery
- Other concomitant laparoscopic or prolapse and anti-incontinence procedures (cystocele repair, rectocele repair or mid-urethral sling procedures) will be performed at the primary surgeon's discretion.
- Patient's must have an up-to-date PAP smear on record, or a PAP smear is performed in the office and verified to be normal pre-enrollment

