**Randomization**

All subjects will be predetermined by their surgeon to undergo a laparoscopic sacrocolpopexy. The participants will then be randomized to either concurrent vaginal hysterectomy or laparoscopic supracervical hysterectomy according to a computer-generated randomization schedule with the use of the SAS statistical software package (SAS Institute, Cary, NC).

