### **Analysis Plan:**

There will be 2 arms to this study: laparoscopic supracervical hysterectomy and sacrocolpopexy with Restorelle® Y mesh and vaginal hysterectomy and sacrocolpopexy using the Restorelle® Dual flat mesh.

We determined that 30 subjects in each arm were needed to detect a difference of 30 minutes or more (standard deviation 30 minutes) in surgical time between the two groups with 80% power and a significance level of .05. We will account for potential subject drop out and loss to follow-up as well as unforeseen factors in recruiting and will plan to recruit 35 subjects to each arm, for a total of 70 subjects.

All statistical analyses will be done using jmp 14. We will use descriptive statistics to show our demographic and baseline data: categorical variables will be presented as n/N (%) with 95% confidence intervals and continuous variables will be presented as mean+/- SD [range]. The two types of hysterectomy (laparoscopic supracervical and vaginal) will be compared. With a continuous outcome and two categorical independent factors, a two-way analysis of variance will be used to evaluate differences between the groups. The results will be presented in a standard ANOVA table, which should be sufficient to determine if differences exist. A linear regression will be done to demonstrate actual changes in surgical time attributed to each variable.

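### Does the one-word exclusion bullet naming the study operation itself leave the trial without a usable eligibility rule?

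*Combined protocol and SAP*

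**What the plan says.** The Exclusion Criteria list six bullets. The fifth, in full, is "Sacrocolpopexy". The bullet before it is a complete condition, "Need for concomitant surgeries not related to pelvic organ prolapse or incontinence", and the one after it excludes women who want to keep the uterus.

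Four other places treat the same operation as a requirement:

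- Inclusion Criteria: adults "who are to undergo laparoscopic sacrocolpopexy for uterovaginal prolapse and desire concurrent hysterectomy at the time of surgery".
- Randomization: "All subjects will be predetermined by their surgeon to undergo a laparoscopic sacrocolpopexy".
- Background and Significance, in the primary objective: "minimally invasive (laparoscopic) sacrocolpopexy performed with concurrent vaginal hysterectomy versus laparoscopic supracervical hysterectomy".
- Analysis Plan, naming the two arms: "laparoscopic supracervical hysterectomy and sacrocolpopexy with Restorelle® Y mesh and vaginal hysterectomy and sacrocolpopexy using the Restorelle® Dual flat mesh".

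The Surgical Interventions section describes the procedure for each arm, with the sacral attachment done laparoscopically in both.

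**The concern.** An exclusion criterion should state a condition that a screener can check. This one names the study procedure and nothing else. Read as written, every woman who meets the first inclusion criterion also meets an exclusion, so the eligible population is empty. Since nobody would run the trial that way, the line presumably stood for something narrower, such as an earlier operation or a different surgical route, and the documents do not say which.

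If the missing restriction mattered, staff at the three hospitals could apply different rules and the enrolled population could not be described exactly. Enrolments also could not be checked cleanly against the written criteria. That is a fair reason to look closely at a single word.

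**Working it through.** No formula applies. The sample size in the Analysis Plan (30 per arm needed, 35 per arm recruited, 70 in total) uses a difference, a standard deviation, a power and a significance level. None of these depends on the bullet. The check is therefore textual.

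**Step 1: count.** There are six exclusion bullets. Five state a complete condition and one does not.

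**Step 2: try each plausible reading and ask whether it would change who is enrolled.**

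| Reading of the bullet | Already settled elsewhere? | Change in enrolment |
|---|---|---|
| Literal: anyone having the operation | Contradicted by the Inclusion Criteria, Randomization and both arms | Would leave nobody, so it cannot be meant |
| An open route | Yes: the Inclusion Criteria and Randomization both require laparoscopic surgery | None |
| A previous sacrocolpopexy | Largely: the woman must have uterovaginal prolapse and want a hysterectomy, so she must still have a uterus | None, or very rare cases |
| A stray fragment of the bullet above | That bullet is complete without it | None |
| A qualifier lost when the PDF was read | The source would then hold the full condition | No defect in the plan |

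The third row needs a further word. The Background says the operation is done for uterovaginal prolapse or for vault prolapse after hysterectomy. Of the first group it says: "In cases of uterovaginal prolapse, hysterectomy is often performed unless uterine preserving surgery is desired and a hysteropexy is performed". Most women with an earlier sacrocolpopexy would therefore have no uterus left to remove and would already fail the inclusion criterion. The exception is a woman who had a uterus-preserving suspension before and now wants a hysterectomy. Nothing in the documents suggests that such women are expected.

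**Step 3: ask whether an unclear case could bias the comparison.** Under Randomization, the surgeon settles on laparoscopic sacrocolpopexy first and allocation follows. The task table puts enrolment and consent at the preoperative visit and randomization on the day of surgery. A doubtful case is thus accepted or refused before the arm is known. The bullet does not mention type of hysterectomy or mesh, so it has no link to either arm.

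**Result.** No reading that can actually be applied alters the treatment contrast, the outcome or the planned number. At most, one could move a rare individual in or out of the trial.

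**The case for a change.** The strongest contrary case is that eligibility criteria define who was studied and, on paper, every enrolled woman breaches one. Screening takes place at three hospitals, so each reader must interpret or ignore the line. Two cases are not plainly closed. One is robotic surgery, which the documents never mention. The other is a previous hysteropexy, because the last bullet, "Patients desiring uterine preservation (hysteropexy)", concerns a present wish and not past surgery. The preoperative items under Data Collection & Management do not name surgical history, so a restriction on earlier operations could not readily be verified from them. Correction would cost one line.

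Part of this stands. The inconsistency is genuine in the text available, the intended meaning cannot be recovered from it, and deleting or completing the line would be reasonable housekeeping that brings the inclusion and exclusion lists into agreement.

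The rest does not carry the point further. Whether robotic assistance counts depends on how the word laparoscopic is read in the Inclusion Criteria, and that question would remain if the bullet were removed. The hysteropexy case is a scenario brought to the text; nothing in the list ties the bullet to earlier surgery. The audit difficulty is formal, because the positive definition of the population is clear and repeated, and enrolments can be checked against that.

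**Conclusion.** The concern does not call for a change to the plan. One of six exclusion bullets is defective as it reads here, and the defect is clerical. The population, the two arms and the order of eligibility before randomization are all fixed by other sections, so correcting the line would change nothing the trial does or concludes. No effect on enrolment, bias, power or the primary comparison is shown.

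This rests on three assumptions. Screeners follow the repeated positive definition and not the impossible literal one. Women with an earlier uterus-preserving suspension are rare among candidates; the documents give no figure, but even if they were common their inclusion would not depend on arm. And the source document does not hold a longer version of the bullet with a substantive restriction. If it does, the bullet has a meaning and the apparent contradiction disappears.

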**Study Procedures:**

**Study Identification and Recruitment**

Potential subjects will be identified by members of the Center for Urogynecology & Pelvic Reconstructive Surgery at the Cleveland Clinic Main campus, Hillcrest Hospital and Fairview Hospital. Eligible patients who agree to participate will be provided written informed consent administered by the collaborators listed on this IRB.

**Randomization**

All subjects will be predetermined by their surgeon to undergo a laparoscopic sacrocolpopexy. The participants will then be randomized to either concurrent vaginal hysterectomy or laparoscopic supracervical hysterectomy according to a computer-generated randomization schedule with the use of the SAS statistical software package (SAS Institute, Cary, NC).

#### Office Interventions

All patients will be seen for a preoperative visit and then postoperatively at 6, 12 and 24 months. The 6 month visit will be standard of care, the 12 month and 24 month visit will be a research visit. At each visit, a vaginal exam and a complete Pelvic Organ Prolapse Quantification (POP-Q) exam will be performed. In addition, patients will be asked to complete the Pelvic Floor Distress Inventory (PFDI-20), Incontinence Severity Index (ISI), Pelvic Organ Prolapse/Urinary Incontinence Sexual Questionnaire (PISQ-12) and Patient Global Impression of Improvement (PGII) questionnaires at the pre-operative visit as well as the 6, 12, and 24 month postoperative visits. Completion of these questionnaires is the only additional assessment that is specific to participation in this study and is not usually included as part of the standard care of sacrocolpopexy. It should take no more than 10-15 minutes to complete the questionnaires. The study subjects will not be exposed to any additional risk by participating in this study except for the inconvenience of completing the questionnaires.

#### Surgical Interventions

The laparoscopic portions of the surgery will be performed using four ports: an umbilical port for the laparoscope (either 5 or 10/12mm), two ports (either 5, 8 or 10/12 mm) in the bilateral lower quadrants, and one 5-mm port placed at the level of the umbilicus, lateral to the rectus muscle on either side for retraction.

If a supracervical hysterectomy is to be performed, it will be done in a standard fashion. A uterine manipulator will be placed inside of the uterus. The round ligaments will be transected using cautery. The fallopian tubes and ovaries will be left in situ or removed at the time of hysterectomy depending upon the preoperative decision made between the surgeon and patient. The uterine arteries and cardinal ligaments will be cauterized laparoscopically. The uterus will be amputated at the level of the internal cervical os and the endocervical canal will be cauterized. The specimen will be extracted in a laparoscopic endocatch bag and removed through an extended incision at the umbilicus at the end of the case. Dissection of the vagina anteriorly and posteriorly will be done laparoscopically with the use of an end-to-end anastomosis (EEA) sizer in the vagina. Dissection of the presacral space will also be done laparoscopically. Five to six 2-0 PDS sutures will be placed to secure the mesh to the anterior vagina as well as the posterior vagina for a total of 10-12 sutures on the vagina; the arm of the mesh will be secured to the anterior longitudinal ligament of the sacrum using two 0 Prolene sutures. The Coloplast® Restorelle Y mesh will be used for all cases. The peritoneum will be closed with 0 or 2-0 vicryl sutures.

If a vaginal hysterectomy is performed, it will be done in a standard fashion using a traditional clamp and suture technique starting at the uterosacral ligaments and ending with the utero-ovarian ligaments. The specimen will be extracted through the vagina. Dissection of the vagina anteriorly and posteriorly will be done vaginally. The mesh will be attached vaginally using five to six 2-0 PDS sutures on the anterior and posterior vagina for a total of 10-12 sutures on the vagina. The Coloplast® Restorelle Dual flat mesh will be used. The vagina will then be closed in two layers using 0 or 2-0 vicryl suture. Laparoscopic entrance will then be gained and set up will be done as described above. The presacral space will be dissected laparoscopically and the mesh attached to the anterior longitudinal ligament of the sacrum using two 0 Prolene sutures. The peritoneum will be closed with 0 or 2-0 vicryl sutures.

### **Data Collection & Management:**

Preoperative data will include the following:

- Patient age, race, vaginal parity, menopausal state, BMI, comorbid conditions, tobacco use, preoperative prolapse stage, preoperative use of vaginal estrogen
- PFDI-20, ISI, PISQ-12

Data points recorded during the procedure will include:

- Total OR time = operating room time of entry and exit
- Surgical time = time from incision to end of sacrocolpopexy (abdominal incisions closed)
- Total Case time = time from incision to end of procedure
- Hysterectomy time = time from start of hysterectomy to end of hysterectomy
- Concomitant procedures
  - Lysis of Adhesions >45 min
  - Anterior colporrhaphy
  - Posterior colporrhaphy
  - Perineorrhaphy
  - Midurethral sling
  - Other
- Estimated blood loss
- Intraoperative complications
  - Vascular Injury
  - Cystotomy
  - Ureteral Injury
  - Bowel Injury - small bowel, large bowel, rectal

Postoperative data will include the following: 6, 12, 24 months

- POP-Q exam (performed by a provider who did not perform the surgery)
- Vaginal exam, inspection for mesh exposure
- PFDI-20, ISI, PISQ-12
- Assessment of use of postoperative vaginal estrogen

- Review of electronic medical record (inpatient notes, d/c summary, ER visits), assessing for postoperative complications
  - Reoperation for immediate complications = reoperation within 30 days of surgery
  - Abdominal Wound infection = fascial, subcutaneous, cutaneous infection requiring antibiotic treatment
  - Hematoma = intrapelvic/abdominal
  - Vaginal cuff cellulitis/Pelvic Abscess = requiring IV/PO antibiotic therapy and/or transvaginal, transgluteal or percutaneous drainage
  - DVT/PE = diagnosed with Doppler US or CT scan
  - Reoperation for SUI with pubovaginal sling (synthetic or fascial), colposuspension, injection with periurethral bulking agents
  - Reoperation for mesh exposure
  - Reoperation for recurrent POP
  - Bowel Injury/Bowel Obstruction = enterotomy, perforation, ileus, partial/complete obstruction
  - Port site or incisional hernia
  - Need for any radiologic imaging
  - Lower urinary tract injury = bladder, ureteral
  - Neurologic Injury = brachial plexus, abdominal wall (ilioinguinal, iliohypogastric), lower extremity (femoral, sciatic, common peroneal)
  - Pulmonary complications = pneumonia, pulmonary hypertension, pulmonary edema within 14 days of surgery
  - Cardiac = ACS, MI, HF within 14 days of surgery
  - Postoperative ICU admission

Protection of each subject's personal health information will be a priority in this study. One master excel file containing subject personal information including name and medical record number will be kept in a password-protected file, on a designated protected research drive on a password-protected computer in a locked office at the Cleveland Clinic. In that file, each subject will be assigned a subject identification number that will be used for the purposes of data collection in order to de-identify subjects.

[figure not shown]
All paper forms used for data collection will be kept in a research cabinet dedicated to this project which will be locked at all times, in a locked office at the Cleveland Clinic. All forms will contain de-identified information – identification numbers will correspond to the subjects listed in the master excel file.

All study data will be transferred and managed electronically using REDCap (Research Electronic Data Capture). Each subject will be entered into REDCap using the assigned identification number from the master excel file. REDCap is a secure, web-based application designed to support data capture for research studies, providing user-friendly web-based case report forms, real-time data entry validation, audit trials, and a de-identified data export mechanism to common statistical packages. The system was developed by a multi-institutional consortium which was initiated at Vanderbilt University and includes the Cleveland Clinic. The database is hosted at the Cleveland Clinic Research Datacenter in the JCN basement and is managed by the Quantitative Health Sciences Department. The system is protected by a login and Secure Sockets Layers (SSL) encryption. Data collection is customized for each study as based on a study-specific data dictionary defined by the research team with guidance from the REDCap administrator in Quantitative Health Sciences at the Cleveland Clinic.

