**Hypothesis:** There is no clinically difference in surgical time in patients undergoing vaginal hysterectomy versus laparoscopic supracervical hysterectomy at the time of sacrocolpopexy

**Study Design:** Randomized trial

**Primary Outcome:** Surgical time defined as time of incision to time of sacrocolpopexy completion (abdominal incisions closed)

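### Uterine size and previous abdominal or pelvic surgery are not listed as baseline data, so the planned table and regression of surgical time cannot use them: a modest loss of precision that is cheap to avoid

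*Combined protocol and SAP*

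**What the plan says.** Under Data Collection & Management, the preoperative items are "Patient age, race, vaginal parity, menopausal state, BMI, comorbid conditions, tobacco use, preoperative prolapse stage, preoperative use of vaginal estrogen", followed by three questionnaires. Uterine size is not among them. Nor is previous abdominal or pelvic surgery: vaginal parity does not capture cesarean, and comorbid conditions do not clearly include surgical history. Neither item appears in the intraoperative list or in the Summary of tasks table, which has only a general demographic row. The eligibility criteria set no limit on uterine size. Apart from a bare exclusion entry for sacrocolpopexy, they do not address previous surgery.

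The nearest recorded item is intraoperative, under concomitant procedures: "Lysis of Adhesions >45 min".

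The primary outcome runs from incision until the abdominal incisions are closed. Both arms remove the uterus within that interval. In the supracervical arm the specimen is "removed through an extended incision at the umbilicus at the end of the case"; in the other arm, "The specimen will be extracted through the vagina".

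Allocation is "according to a computer-generated randomization schedule with the use of the SAS statistical software package", with no stratification factor stated. The Analysis Plan describes baseline tables, a two-way analysis of variance whose second factor is not named, and a linear regression of surgical time with no list of covariates.

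**The concern.** The outcome is the duration of an operation that removes the uterus and works laparoscopically in the pelvis. The size of the uterus and the presence of adhesions from earlier surgery are plausible determinants of that duration. The plan itself provides a box for adhesiolysis longer than 45 minutes, which exceeds the whole 30-minute target difference. Several listed items (tobacco, vaginal estrogen, parity) seem better suited to the mesh and prolapse outcomes than to operating time.

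With about 35 women per arm and no stratification, the arms may differ by chance on either factor, and a reader of the planned baseline table could not tell. The hypothesis is of no clinically important difference, so interpretation will depend on the width of the interval around a possibly small estimate. Baseline variables that predict the outcome are a cheap way to narrow that interval, and these two are not on the list.

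**Working it through.** **Inputs from the Analysis Plan.** SD 30 min, target difference 30 min, 80% power, significance level 0.05 (taken as two-sided), 35 recruited per arm.

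**Assumed input.** R², the share of within-arm variance in surgical time explained by the two missing items together. The documents give no figure; 10%, 20% and 30% are used.

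**1. The plan's own sample size.** The plan states that "30 subjects in each arm were needed". From its inputs, n = 2 × (1.960 + 0.842)² × 30²/30² = 15.7, so 16 per arm (17 by the t-test). The stated 30 does not reproduce; it gives about 97% power. That is a separate matter, but it shows that power for a 30-minute difference is not scarce: at 35 per arm it is about 98%.

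**2. Unadjusted precision.** SE = 30 × √(2/35) = 7.17 min. The 95% half-width is 1.995 × 7.17 = 14.3 min (68 df).

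**3. Share of that uncertainty due to chance imbalance in the two items.** SD of the shift = √R² × 7.17; 95% range = 1.96 × that SD.

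| R² | SD of shift (min) | 95% range (min) |
|---|---|---|
| 10% | 2.27 | ±4.4 |
| 20% | 3.21 | ±6.3 |
| 30% | 3.93 | ±7.7 |

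These ranges are a component of the ±14.3 min in step 2 and are not added to it.

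**4. Adjusted precision.** Half-width = 1.997 × 7.17 × √(1 − R²) × √(68/66). The t quantile has 66 df, and the last factor (1.015) allows approximately for estimating two more coefficients. The equivalent increase in sample size is (14.31 / adjusted half-width)² − 1.

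| R² | Half-width (min) | Gain (min) | Equivalent extra women |
|---|---|---|---|
| 10% | 13.8 | 0.5 | 8% |
| 20% | 13.0 | 1.3 | 21% |
| 30% | 12.2 | 2.2 | 38% |

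The simple ratio 1/(1 − R²) would give 11%, 25% and 43%, but it ignores the degrees of freedom spent. At R² = 5% the gain is only about 0.15 min.

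**5. How often a visible imbalance would arise.** Suppose 40% of women have had previous surgery (assumption). The exact binomial probability that arms of 35 differ by 7 women or more (20 percentage points) is 0.112. Over prevalences of 20% to 50% it runs from 0.051 to 0.120. If such a factor alone explained 10% of the variance, its effect would be √(0.10 × 900 / (0.4 × 0.6)) = 19.4 min, and a 20-point imbalance would move the estimate by 0.2 × 19.4, about 4 min.

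**6. Can recorded data stand in?** Adhesiolysis is observed after allocation. It may depend on the arm, because one arm does its hysterectomy and vaginal dissection laparoscopically, and the item misses anything up to 45 minutes. It is not a sound covariate for the arm comparison. Pathology weight is not directly comparable between arms: the supracervical specimen is amputated at the internal os, while the vaginal specimen includes the cervix. The documents do not say how large that difference is.

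**The case against.** The strongest reply is that randomization already handles the problem. The standard error of the unadjusted comparison covers chance imbalance in every unmeasured factor, so there is no bias. A reader might infer from the ±4.4 to ±7.7 min range that the primary result could be off by that much beyond its confidence interval. The documents do not support this, because that range already lies inside the 14.3 min half-width. This part of the reply stands in full.

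A reader might also infer that operative difficulty could neither be seen nor adjusted for. That goes too far. BMI, prolapse stage and comorbid conditions are recorded and plausibly reflect difficulty in part. Previous surgery is a fixed fact from before allocation; the master file holds medical record numbers, so it could be retrieved later if charted. Uterine size is harder to recover if nobody recorded it before the operation. This stands too and limits the point to two named items.

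Third, the gain is small against a 30-minute target and rests on an assumed R². This is also correct.

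Fourth, the Analysis Plan commits no variable to the primary model, and choosing these two over surgeon, site or concomitant procedures is partly judgment. That is fair, and it means the new fields improve precision only if the covariates are prespecified. It does not remove the point: neither item is in any data list, and adding them requires no new procedure.

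**Conclusion.** The omission is real, and its consequence is modest. Uterine size and previous abdominal or pelvic surgery are absent from every data list, so the baseline table and the regression cannot use them as planned. The primary comparison remains valid without them.

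The cost is 0.5 to 2.2 min of 95% half-width, or the precision of about 8-38% more women, together with a less informative baseline table when a small difference has to be interpreted. These figures rest on the plan's SD of 30 min, 35 women per arm with surgical time recorded, and the assumption that the two items explain 10-30% of the variance. Below that range the benefit nearly vanishes. Severity is minor: an inexpensive improvement, not a flaw that threatens the conclusion.

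**What to change.** Under Data Collection & Management, add two preoperative fields:

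- **Uterine size**, from the preoperative examination or existing imaging. Office Interventions already states: "At each visit, a vaginal exam and a complete Pelvic Organ Prolapse Quantification (POP-Q) exam will be performed". The Summary of tasks table appears to mark POP-Q but not the vaginal exam at the preoperative visit, so that row should be brought into line.
- **Previous abdominal or pelvic surgery, including cesarean** (yes/no and number), from the chart.

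Record both before randomization. The tasks table places randomization on the day of surgery, so the preoperative visit suffices. Show both by arm in the baseline table.

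In the Analysis Plan, name both in advance as covariates in the linear model that estimates the arm difference in surgical time, each entered as a single term, and state the model's full covariate list. Do not adjust that comparison for intraoperative adhesiolysis, which is observed after allocation.

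The cost is two form fields, one sentence in the Analysis Plan and two degrees of freedom. Uterine size on examination is approximate, which will reduce the variance it explains and hence the gain.
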